9.1.5. ACURATE Continued Access Study Subjects

For the ACURATE Continued Access Study, subjects confirmed eligible for the study by the CRC (see Section **21.2**) and who provided written informed consent (see Section **20**) are considered enrolled in the study as soon as an attempt is made to insert the test device into the subject's femoral artery.

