Assessment	Screening ^a	Baseline	Procedure	Within 1 Day Post- procedure	Prior to Discharge or 7 Days Post- Procedure	30 Days ^b (±7 Days) Office/ Telehealth Visit	6 Months ^b (±30 Days) Office/ Telehealth Visit	1 Year ^b (±30 Days) Office/ Telehealth Visit	2–5 Years ^b [Annual] (±45 Days) Office/ Telehealth Visit	7 and 10 Years ^b (±60 Days) Office/ Telehealth Visit	6, 8, and 9 Years ^b (±60 Days) Telephone
Procedural cine- angiography with post- deployment aortogram ^o	_	_	х	_	_	_	_	_	_	_	_
Balloon aortic valvuloplasty ^p	_	-	X/O	_	_	_	_	_	_	_	—
AE and ADE assessments ^q	_	_	х	х	х	Х	Х	Х	_	_	_
Device deficiencies, SAE, SADE, UADE and CEC event assessments ^r	_	_	х	х	х	х	х	Х	Х	Х	Х
4D CT imaging of prosthetic valve ^s	_	_	_	_	_	Х	_	Х	_	_	_

Table 10.1-1: Data Collection Schedule for ACURATE IDE

Note: X = required; O = optional; - = not required; follow-up should be done by study personnel or as noted below. Visits at 30 days, 6 months, 1–5 years, 7 years and 10 years are office/clinical/in-person or telehealth visits; all required ECG measurements and TTE measurements must be done for all subjects who have a transcatheter valve implanted in the aortic position during the index procedure, even if the associated follow-up assessment is carried out via telehealth.

a: Screening materials for CRC review should be submitted electronically at least 5 days in advance of CRC review.

- b: All follow-up dates will be calculated from the date of the (attempted) index procedure (or from date of randomization for randomized subjects where no implant is attempted). Where indicated, visits must be an office/clinical/in-person visit but may be done in-hospital should the subject be admitted at the time. Subjects who are enrolled but do not receive a study device (test or control) will be followed for 1 year to assess for safety but do not need to have protocol required TTE, ECG or QOL assessments.
- c: Study-specific consent includes screening consent to perform required assessments beyond standard of care that will be evaluated by the CRC to confirm subject eligibility. If the study Informed Consent Form is modified during the course of the study, study subjects will be re-consented as necessary.

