- k: A CT angiogram of the aortic complex must be performed within 180 days prior to CRC approval (and should be performed within 90 days if possible) to evaluate the aortic valve anatomy and aortic root dimensions for device sizing. CT angiogram must be performed according to the CT/Angiography Core Laboratory procedure guidelines (see study Manual of Operations). It must be sent to the core laboratory for detailed measurements and analyses in advance of the CRC review where results will be assessed to confirm subject's eligibility.
- 1: An assessment of the iliofemoral system must be performed within 180 days prior to CRC approval (and should be performed within 90 days if possible). A CT angiogram of the iliofemoral system should be performed for complete visualization of the iliac and femoral arteries to assess for dimensions, tortuosity, and calcification. The CT angiogram should be performed per the procedure guidelines (see study Manual of Operations) and sent to the CT core laboratory with the screening CT angiogram of the aortic structure. An iliofemoral invasive angiogram may be substituted for the iliofemoral CT angiogram.
- m: Includes the Kansas City Cardiomyopathy and SF-12 QOL questionnaires. Baseline QOLs must be performed within 30 days prior to the index procedure.
- n: QOL survey at 5 years.
- o: Procedural cine-angiogram including the baseline images of the aortic complex and the final post-deployment aortogram of the ascending aorta must be performed and sent to the CT/Angiography core laboratory for analysis.
- p: Balloon aortic valvuloplasty following standard techniques must be performed with an appropriately sized valvuloplasty balloon before test device implantation; BAV may be performed before control device implantation, but planned use should be reviewed by the CRC.
- q: In subjects who receive a study device, AEs and ADEs will be monitored and collected from the time of enrollment through 12-month follow-up. For subjects who do not receive a study device, AEs will be monitored through 12-month follow-up.

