11.2.1. Analysis Sets

The primary endpoint and additional measurements will be analyzed on an ITT and an implanted basis.

Confidential

Subjects in the randomized cohorts (Main Randomized Cohort and Extended Durability Study) are considered enrolled in the study upon randomization. Among the randomized cohorts, for ITT analyses, all subjects who sign the IRB/REB/HREC/ IEC-approved study ICF (see Section **10.3**), are enrolled in the trial, and are randomized will be included in the analysis, whether or not an assigned study valve (ACURATE or Control) was implanted. For implanted analyses, ITT subjects who had the assigned (Test versus Control), randomized study valve implanted will be included in the analysis. For the implanted randomized cohort analysis sets, if a subject receives 2 different valve types from 2 different manufacturers, the subject will be excluded from the implanted analysis.

With the Roll-In, ACURATE *Prime*[™] XL Nested Registry, and ACURATE CAS cohorts, the subject is considered enrolled in the trial when there is an attempt made to insert the ACURATE Transfemoral Aortic Valve System into the subject's femoral artery. For ITT analyses, all subjects who sign the IRB/REB/HREC/IEC-approved study ICF and are enrolled in the trial will be included in the analysis sample, regardless of whether the study device was implanted. The implanted population includes all subjects who sign an ICF and are implanted with an ACURATE valve.

For the Main Randomized Cohort, the primary endpoint will be analyzed for the ITT and implanted analysis sets. The primary analysis for the primary endpoint will be based on the ITT analysis set.

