11.2.5. Reporting Events

For all subjects in the ACURATE IDE Roll-In, ACURATE *Prime*[™] XL Nested Registry, and ACURATE CAS cohorts, all events that occur from the time of enrollment will be reported. For all subjects in the ACURATE IDE randomized cohorts (Main Randomized Cohort and Extended Durability Study), events from the time of randomization onward will be reported.

For randomized subjects who do not have an attempted procedure, events from the date of randomization to 1-year post-randomization will be reported. For subjects who are enrolled and have an attempted procedure but do not receive a study valve, events from the index procedure to 1-year post procedure will be reported.

For time-based clinical events, the cut-off for events for 30-day endpoints will be 30 days, for 6-month endpoints it will be 180 days, for 1-year endpoints it will be 365 days, and for endpoints at 2-10 years it will be 365 days times the number of years. For events at discharge or 7 days post-procedure, the cut-off for events will be the earlier of the date of discharge or 7 days post-procedure for each subject.

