19.1. Reportable Events by Investigational Center to Boston Scientific

It is the responsibility of the investigator to assess and report to BSC any event that occurs in any of the following categories; reporting requirements are described below in **Table 19.4-1**.

- All serious adverse events
- All adverse events and adverse device effects (through 12 months)
- All investigational device deficiencies
- Unanticipated adverse device effects/unanticipated serious adverse device effects
- New findings/updates in relation to already reported events

When possible, the medical diagnosis should be reported as the Event Term instead of individual symptoms.

If it is unclear whether or not an event fits one of the above categories, or if the event cannot be isolated from the device or procedure, it should be submitted as an adverse event and/or device deficiency.

Any reportable event required by the protocol, experienced by the study subject after informed consent and once considered enrolled in the study, whether during or subsequent to the procedure, must be recorded in the eCRF.

Underlying diseases are not reported as AEs unless there is an increase in severity or frequency during the course of the investigation. Death should not be recorded as an AE but should only be reflected as an outcome of one (1) specific SAE (see **Table 19.2-1** for AE definitions).

In-patient hospitalization is defined as the subject being admitted to the hospital, with the following exceptions.

- A hospitalization that is uncomplicated and elective/planned (i.e., planned prior to enrollment) does not have to be reported as an SAE.
- If complications or AEs occur during an elective/planned (i.e., planned prior to enrollment) hospitalization after enrollment, the complications and AEs must be reported as AEs or SAEs if they meet the protocol-specified definitions.

For the randomized cohort, event reporting (eCRF data entry) is required beginning from the time of randomization. For the Roll-In and ACURATE *Prime* XL Nested Registry cohorts, event reporting (eCRF data entry) is required beginning from the time an attempt is made to insert the ACURATE Transfemoral Aortic Valve System into the subject's femoral artery.

Refer to Section 18 for the known risks associated with the study devices (test and control).

Based on the VARC^{66,67} recommendations and definitions, the adverse events and/or safety endpoints requiring adjudication by the CEC include the following.

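### Single-arm cohorts: when a procedure stops between arterial puncture and attempted ACURATE insertion, SAE and CEC reporting is not clearly required

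*Protocol*

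**What the plan says.** **Enrolment.** Protocol 9.1.1, 9.1.3 and 9.1.5 use the same rule for Roll-In, Prime XL and Continued Access: a confirmed, consented subject is "considered enrolled in the study as soon as an attempt is made to insert the test device". Protocol 11.2.1 repeats it for the analysis sets ("the subject is considered enrolled in the trial when there is an attempt made to insert the ACURATE Transfemoral Aortic Valve System"), as does SAP 4.2.

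**Start of reporting.** Protocol 19.1 requires eCRF recording of a reportable event "experienced by the study subject after informed consent and once considered enrolled in the study". For Roll-In and Prime XL it adds that "event reporting (eCRF data entry) is required beginning from the time an attempt is made to insert the ACURATE Transfemoral Aortic Valve System". That sentence does not name Continued Access. Protocol 11.2.5 covers all three cohorts: "all events that occur from the time of enrollment will be reported". For subjects enrolled with an attempted procedure but no valve, 11.2.5 uses a different start: "events from the index procedure to 1-year post procedure will be reported". Table 10.1-1 footnote r limits SAE and CEC reporting to enrolled subjects, counted from enrolment.

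**Subjects without a device.** Footnote b reads: "Subjects who are enrolled but do not receive a study device (test or control) will be followed for 1 year to assess for safety". Footnote q is looser: "For subjects who do not receive a study device, AEs will be monitored through 12-month follow-up". Table 6.4-1 asks for a modified Rankin score after a neurological event in subjects with an attempted procedure and no implant.

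**Analysis window.** SAP 4.2 and 7.3.3 count single-arm events from the procedure date.

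**The concern.** Invasive steps that the protocol itself requires come before the point at which a single-arm subject is enrolled. A vascular injury at sheath placement, or a stroke, annular injury or tamponade at BAV, could end the procedure before the delivery catheter is introduced. Read literally, the enrolment-based rules leave that subject outside the ITT set and outside the SAE and CEC reporting duty.

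What is at stake is complete safety accounting. Vascular access success is one of the device-performance measures (Protocol 6.4, SAP 5.2), yet a subject whose access fails before attempted insertion never enters the single-arm set. The Data Monitoring Committee oversees adverse events (Protocol 21.1.2) but may not see these. Protocol 7.1 says that Continued Access data will serve to assess performance and safety further.

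**Working it through.** No power or error-rate calculation applies, and the plan gives no figure to reproduce. The check sets the texts side by side.

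1. **What is inserted at enrolment.** Protocol 10.7.2.2 defines the ACURATE system as the valve plus its transfemoral delivery system. The iSLEEVE introducer is a separate accessory (5.1.3). Placing the sheath is therefore not an attempt to insert the system.
2. **Order of steps.** The sheath goes into the femoral artery (10.7.2). BAV is compulsory before ACURATE implantation, and hemodynamic status is checked before the system is introduced (10.7.2.1). The system catheter then enters the introducer (10.7.2.2). Puncture, sheath and BAV thus lie before enrolment.
3. **Can a procedure stop in that window?** Protocol 10.3 provides for a consented subject found ineligible during the procedure. That subject is a screening failure, recorded on the screening module, and the text does not ask for harms.
4. **Who must be reported if it does.** Sections 19.1 and 11.2.5 and footnotes b and r all require enrolment. Footnote q's second sentence has no enrolment condition, but it concerns AEs; SAE and CEC reporting sits in footnote r. Table 6.4-1 covers neurological events only. SAP 4.2 counts from the procedure date, but its single-arm ITT set holds only enrolled subjects. Coverage is partial.
5. **Subjects who do reach insertion.** Table 10.1-1 marks AE, SAE and CEC assessment in the Procedure column. The procedure-data list in 10.7.2.2 includes the same assessments. Protocol 11.2.5 goes back to the index procedure for enrolled subjects without a valve, and SAP 4.2 and 7.3.3 count from the procedure date. Same-day sheath and BAV harms are therefore largely captured; what remains is that the start times in 19.1 and 11.2.5 disagree with SAP 4.2.
6. **Reach of the rule.** Planned single-arm enrolment is up to 170 + 50 + 1000 = 1220 of 2820 subjects (1220/2820 = 43%). This is the number governed by the rule, not the number affected. The documents give no count of procedures stopped between puncture and insertion.
7. **Direction for event rates.** Let N enrolled subjects have event proportion p, and let m stopped subjects have event proportion q. Including the stopped subjects gives (Np + mq)/(N + m), which differs from p by m(q − p)/(N + m). The sign is that of q − p. Neither m nor q can be found in the documents, so neither sign nor size can be stated. For counts the direction is fixed: leaving out a harm or an access failure can only lower the count.
8. **Hypothesis tests.** The primary endpoint uses the Main Randomized Cohort, where events are reported from randomization. The Prime XL gradient test and the QoL test use implanted subjects. A subject stopped before insertion belongs to none of these analyses.

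**The case against.** The best defence is that this is a consistent, disclosed design choice: exposure is defined by attempted use of the investigational system, in the same terms throughout both documents. Roll-In and Continued Access are descriptive, with no inference planned. Late access failures should be uncommon, because iliofemoral imaging is reviewed by the Case Review Committee (10.4), transfemoral suitability is required beforehand (10.7), and EC20 and EC21 exclude unsuitable access. All of that stands, and it keeps the point minor.

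Other texts give some further cover. Protocol 10.10 follows subjects who receive a surgical valve to study end without repeating the enrolment condition, though its context is enrolled subjects. Section 19.1 asks sites to submit events that cannot be separated from device or procedure, but that helps to classify an event; it does not widen whose events are reportable. Section 20 keeps a log of candidates who fail entry criteria, without asking for harms. None of these closes the gap.

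A reader might also infer more than the documents support:

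- **That every omission flatters the device.** This holds for counts of harms and access failures. It does not follow for event rates, because event-free stopped subjects are left out too.
- **That 10.7 proves pre-insertion stops are expected.** Its sentence on an unsuccessful transfemoral approach also fits a failed insertion or advancement of the delivery system, when the subject is already enrolled. Only 10.3 clearly reaches the window, and it concerns ineligibility rather than complications.
- **That sheath and BAV harms go missing in treated subjects.** Step 5 of the working shows that they are largely captured.

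**Conclusion.** The gap is real but narrow. For a consented Roll-In, Prime XL or Continued Access subject whose procedure stops between puncture and attempted insertion, SAE and CEC reporting is not clearly required. Harm and access-failure counts for these cohorts can be understated as a result. The number of such procedures is not given; it is probably small, but that is a judgement. No effect on event rates can be signed or sized, and no hypothesis test, including the primary endpoint, is touched. For subjects who reach insertion, the issue is only a conflict of wording over when reporting starts.

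The conclusion rests on reading the ACURATE system as valve plus delivery catheter, as 10.7.2.2 defines it, and on the enrolment conditions in 19.1, 11.2.5 and footnote r meaning what they say. Sites may in practice report such events anyway; the documents do not oblige them to. This is a minor, cheap improvement to safety accounting.

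**What to change.** 1. In Protocol 19.1 (naming Continued Access), 11.2.5 and Table 10.1-1 footnotes q and r, start single-arm event reporting at arterial puncture for the TAVR sheath. That time is already among the procedure data in 10.7.2.2, and the change agrees with the procedure-date rule in SAP 4.2.
2. For consented subjects punctured without an insertion attempt, record procedural AE, SAE and CEC events through discharge or 7 days, whichever comes first. Longer follow-up is optional: a full year for people who were never enrolled would create a new followed population, and the point does not need it.
3. List these subjects and their events separately, beside the ITT set. The enrolment definition and the ITT set stay as they are.

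The cost is wording changes in the Protocol, a line in the SAP for the listing, a little more data entry and one small extra listing. Descriptive single-arm reporting may look slightly less favourable.

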19.2. Definitions and Classification

Adverse event definitions are provided in **Table 19.2-1**. Administrative edits were made on the safety definitions from ISO 14155 and MEDDEV 2.7/3 for clarification purposes.

Term	Definition	
Adverse Event (AE) Ref: ISO 14155 Ref: MEDDEV 2.7/3	Any untoward medical occurrence, unintended disease or injury, or any untoward clinical signs (including an abnormal laboratory finding) in subjects, users or other persons, whether or not related to the investigational medical device.	
Ref. MEDDEV 2.7/5	Note 1: This includes events related to the investigational medical device or comparator.	
	Note 2: This definition includes events related to the procedures involved.	
	Note 3: For users or other persons, this definition is restricted to events related to the investigational medical device.	
Adverse Device Effect (ADE) Ref: ISO 14155 Ref: MEDDEV 2.7/3	Adverse event related to the use of an investigational medical device Note 1: This includes any adverse event resulting from insufficiencies or inadequacies in the instructions for use, the deployment, the implantation, the installation, the operation, or any malfunction of the investigational medical device.	
	Note 2: This definition includes any event resulting from use error or intentional abnormal use of the investigational medical device.	
Serious Adverse Event (SAE)	Note 1: This definition meets the reporting objectives and requirements of ISO 14155 and MEDDEV 2.7/3.	
Ref: ISO 14155	Adverse event that:	
Ref: MEDDEV 2.7/3	a) Led to death,	
	b) Led to serious deterioration in the health of the subject as defined by either:	
	1) a life-threatening illness or injury, or	
	2) a permanent impairment of a body structure or a body function, or	
	3) in-patient hospitalization or prolongation of existing hospitalization, or	

 Table 19.2-1: Safety Definitions

Term	Definition	
	 4) medical or surgical intervention to prevent life-threatening illness or injury or permanent impairment to a body structure or a body function c) Led to fetal distress, fetal death, or a congenital abnormality or birth defect. 	
	Note 2: Planned hospitalization for a pre-existing condition, or a procedure required by the clinical investigational plan, without a serious deterioration in health, is not considered a serious adverse event.	
Serious Adverse Device Effect (SADE) Ref: ISO 14155 Ref: MEDDEV 2.7/3	Adverse device effect that has resulted in any of the consequences characteristic of a serious adverse event.	
Unanticipated Adverse Device Effect (UADE) Ref: 21 CFR Part 812	Any serious adverse effect on health or safety or any life-threatening problem or death caused by, or associated with, a device, if that effect, problem, or death was not previously identified in nature, severity, or degree of incidence in the investigational plan or application (including a supplementary plan or application), or any other unanticipated serious problem associated with a device that relates to the rights, safety, or welfare of subjects.	
Unanticipated Serious Adverse Device Effect	Serious adverse device effect which by its nature, incidence, severity, or outcome has not been identified in the current version of the risk analysis report.	
(USADE) Ref: ISO 14155 Ref: MEDDEV 2.7/3	Note: Anticipated serious adverse device effect (ASADE) is an effect which by its nature, incidence, severity or outcome has been identified in the risk analysis report.	
Serious Health Threat Ref: ISO 14155	Signal from any adverse event or device deficiency that indicates an imminent risk of death or a serious deterioration in the health of subjects, users or other persons, and that requires prompt remedial action for other subjects, users or other persons.	
	Note 1: This would include events that are of significant and unexpected nature such that they become alarming as a potential serious health hazard or possibility of multiple deaths occurring at short intervals.	
Device Deficiency Ref: ISO 14155 Ref: MEDDEV 2.7/3	An inadequacy of an investigational medical device related to its identity, quality, durability, reliability, safety or performance. This may include malfunctions, use error, or inadequacy in the information supplied by the manufacturer.	
The following definitions classification purposes:	s will be used for defining hospitalization or prolongation of hospitalization for SAE	
Hospitalizations	Hospitalization does not include:	
	• Emergency room visit that does not result in in-patient admission	
	Note 1: Although an emergency room visit does not itself meet the definition for hospitalization, it may meet other serious criteria (e.g., medical or surgical intervention to prevent permanent impairment or damage)	
	• Elective and pre-planned treatment/surgery for a pre-existing condition that is documented in the subject's record at the time of consent/enrollment	

Table 19.2-1: Safety Definitions

Term	Definition	
	• Admission for social reasons and/or respite care in the absence of any deterioration in the subject's general condition (e.g., subject is homeless, caregiver relief)	
	Pre-planned, protocol-specified admission related to the clinical study (e.g., procedure required by protocol)	
Prolongation of Hospitalization	In-patient admission to the hospital that is prolonged beyond the expected standard duration for the condition under treatment.	
	Note 1: New adverse events occurring during the hospitalization are evaluated to determine if they prolonged hospitalization or meet another SAE criterion.	

19.3. *Relationship to Study Device(s)*

The Investigator must assess the relationship of the reportable AE/SAE to the study device and procedure. See criteria in **Table 19.3-1**:

Table 19.3-1: Criteria for Assessing Relationship of Study Device and Procedure to
Adverse Event

Classification	Description	
Not Related	Relationship to the device or procedures can be excluded when:	
Ref: MEDDEV 2.7/3	• the event is not a known side effect of the product category the device belongs to or of similar devices and procedures;	
	• the event has no temporal relationship with the use of the investigational device or the procedures;	
	• the serious event does not follow a known response pattern to the medical device (if the response pattern is previously known) and is biologically implausible;	
	• the discontinuation of medical device application or the reduction of the level of activation/exposure - when clinically feasible – and reintroduction of its use (or increase of the level of activation/exposure), do not impact on the serious event;	
	• the event involves a body-site or an organ not expected to be affected by the device or procedure;	
	• the serious event can be attributed to another cause (e.g. an underlying or concurrent illness/ clinical condition, an effect of another device, drug, treatment or other risk factors);	
	• the event does not depend on a false result given by the investigational device used for diagnosis, when applicable; harms to the subject are not clearly due to use error;	
	In order to establish the non-relatedness, not all the criteria listed above might be met at the same time, depending on the type of device/procedures and the serious event.	

Table 19.3-1: Criteria for Assessing Relationship of Study Device and Procedure to
Adverse Event

Classification	Description	
Unlikely Related Ref: MEDDEV 2.7/3	The relationship with the use of the device seems not relevant and/or the event can be reasonably explained by another cause, but additional information may be obtained.	
Possibly Related Ref: MEDDEV 2.7/3	The relationship with the use of the investigational device is weak but cannot be ruled out completely. Alternative causes are also possible (e.g. an underlying or concurrent illness/ clinical condition or/and an effect of another device, drug or treatment). Cases where relatedness cannot be assessed, or no information has been obtained should also be classified as possible.	
Probably Related Ref: MEDDEV 2.7/3	The relationship with the use of the investigational device seems relevant and/or the event cannot be reasonably explained by another cause, but additional information may be obtained.	
Causal Relationship Ref: MEDDEV 2.7/3	The serious event is associated with the investigational device or comparator or with procedures beyond reasonable doubt when:	
	• the event is a known side effect of the product category the device belongs to or of similar devices and procedures;	
	• the event has a temporal relationship with investigational device use/application or procedures;	
	• the event involves a body-site or organ that	
	- the investigational device or procedures are applied to;	
	- the investigational device or procedures have an effect on;	
	• the serious event follows a known response pattern to the medical device (if the response pattern is previously known);	
	• the discontinuation of medical device application (or reduction of the level of activation/exposure) and reintroduction of its use (or increase of the level of activation/exposure), impact on the serious event (when clinically feasible);	
	• other possible causes (e.g. an underlying or concurrent illness/ clinical condition or/and an effect of another device, drug or treatment) have been adequately ruled out;	
	• harm to the subject is due to error in use;	
	• the event depends on a false result given by the investigational device used for diagnosis, when applicable	
	In order to establish the relatedness, not all the criteria listed above might be met at the same time, depending on the type of device/procedures and the serious event.	

